Can We Alleviate Pain Associated With The Peripheral Intravenous Catheterisation By Using Distraction Methods in Adults? A Randomised Controlled Trial

Study Protocol and Data Analysis

1. Aims

This study aimed to determine the effect of methods of distraction to mitigate pain associated with the PIC insertion procedure, thus improving patient satisfaction. Specifically, we examined such effect by playing 3D videos with virtual reality (VR) goggles and showing pictures to the patient containing distractive optical illusions. The study's hypotheses were as follows:

- a. Pictures including optical illusion and 3D video display with VR goggles reduce pain associated with needle entry during the PIC procedure compared to the control group.
- b. Pictures including optical illusion and 3D video display with VR goggles increase the satisfaction during the PIC procedure compared to the control group.

2. Study Design and Setting

The research was performed with a randomised controlled single-blind quasi-experimental study. It was conducted at the emergency unit of a training and research hospital in Ankara, Turkey, between January 18 and April 30, 2018. Before the PIC insertion, the patients were assigned to three groups.

Group-1 (Control): No intervention was made during PIC insertion.

Group-2 (Cards containing optical illusion pictures): Cards containing approximately six optical illusion pictures were shown to the patients and as a method of distraction during the PIC insertion procedure they were asked what they saw in these cards. Showing these cards

started at the beginning of the PIC insertion procedure and lasted approximately 2-3 minutes. (Seckel & Hofstadter, 2004).

Group-3 (3D Video): Underwater 3D audial videos were played with visual reality (VR) goggles during PIC insertion until the procedure was completed. This show, starting at the beginning of the procedure, lasted nearly 2-3 minutes. VR goggles were used for 3D video playing in the research. VR goggles were applied by means of smart phones. After mobile phone placement in the pull chamber at the front side of the VR goggle, it was attached by a headband. The distance between the mobile phone and the object was adjusted specifically for the patient, and patient comfort was taken into account.

3. Participants

The study sample consisted of 120 patients aged between 18 and 65 years old, who ranked 4 (less urgent) and 5 (non-urgent) based on Canadian Emergency Department Triage and who had no visual, audial, or lingual disabilities, and no mental disorder. Only those patients who planned to have PIC insertion and were suitable for having PIC insertion at their antecubital location using 20 Gauge (pink) cannula were eligible. Patients who applied to the emergency service for acute pain and had not used analgesics within 24 hours before applying to the emergency service or had previously experienced multiple PIC procedures, were excluded from the research scope. Patients who refused to participate in the study, who were not eligible for 20 G PIC insertion, who were not in the age range of 18-65 years, and who could not be inserted PIC at the first time (n=98) were excluded from the study (Figure 1). The CONSORT checklist was followed in reporting this study.

4. Sample Size Calculation

The sample size was estimated by using the Medicres E-piccos program (<https://www.e-piccos.com/apps/power/sscm>), and it was determined that a minimum of 117 patients were

needed [d (effect size/ effect width) =1.60, α =0.05, β =0.10, and power=0.95]. The study sample numbered 120 patients.

5. Randomisation

The randomisation method was used by layering according to gender. The patients were distributed into groups using the Medicres E-piccos randomisation program (<https://www.e-piccos.com/apps/calculation/rapg>). Three groups of 40 patients each were generated, and 120 patients were randomised into the control or experimental groups.

6. Data Collection Tools

The data were collected in the study scope by means of a data collection form consisting of the socio-demographic characteristics of the patients and the visual analog scale (VAS). VAS was used to evaluate pain caused by needle insertion. In the VAS of 10 cm length, “0” indicated no pain, and “10” indicated the severest pain. The scale between 1 and 10 was used to evaluate levels of satisfaction with the procedure. In this scale, “1” indicated the level of least satisfaction and “10” indicated the highest satisfaction level. The patients marked their pain and satisfaction levels on this scale.

7. PIC Insertion Procedure

The patient was seated in a position that suited the procedure. The arms were positioned below the heart level, when possible. An area in the antecubital location with no skin lesion was selected for PIC. The antecubital area and back of the hand are mostly preferred for the PIC. Because the antecubital vein, which is more commonly used in the PIC applications, has been reported to be less painful than the veins in the back of the hand in the literature, the PICs were all applied to the antecubital vein in the left arm. An autoguard shielded PEU-Vialon (BD-Venflon, Becton Dickinson) was used as an PIC. Lateral holding sections of the cannula were positioned horizontally. The tourniquet was attached to the patient’s outfit at 5-12 cm above the selected vein. The patient was asked to open and close his/her hand and

make a fist. The veins in the arm used for application were monitored and palpated. The selected location was cleaned by antiseptic solution and 1-2 minutes were allowed for drying. The PIC was held as the blade of the needle was facing upward. A location approximately 3-5 cm below the point of insertion was pressed near the thumb of the empty hand to stabilize the vein, and the skin was stretched downwards. When the needle was inserted into the vein, the plastic portion was gently pushed through the inside of the vein. The tourniquet was undone and the catheter was fixed on the skin with a plaster. This application was completed within approximately 2-3 minutes. All of the PIC insertion procedures were performed by the same researcher. The other researcher, who did not know which patient was in which group, collected the data on the assessment of PIC procedure-associated pain and satisfaction levels immediately after PIC insertion using face-to-face interviews.

8. Ethical Consideration

A permit (number 18/7 and dated 10/16/2018) from the Ethical Committee of the hospital where the research was conducted was received, and the hospital's written permission was obtained. Moreover, the procedures to be carried out were explained to the patients prior to the procedure, and their written and oral consents were received.

9. Data Analysis

The collected data were analyzed by using the SPSS 21.0 package program. The variables determined by counting were shown in numbers and percentages, and the variables determined by measurements were shown as averages and standard deviations. T test and One way ANOVA were used in comparative statistics. A $p < 0.05$ level was accepted as an indication of significant difference in statistical decisions.

Figure-1. Diagram showing the flow of participants.

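### Does the tangled acute-pain and analgesic exclusion in section 3 undermine the needle-pain comparison?

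*Protocol*

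**What the plan says.** The Protocol, section 3 (Participants), puts three conditions into one exclusion sentence. It begins "Patients who applied to the emergency service for acute pain and", continues with "had not used analgesics within 24 hours before applying to the emergency service", and ends "or had previously experienced multiple PIC procedures, were excluded from the research scope". No bracket, list or repeated subject shows how the *and* and the *or* group.

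The next sentence gives further exclusions: refusal, unsuitability for the 20 G cannula, age outside 18 to 65 and failure at the first attempt, ending "who could not be inserted PIC at the first time (n=98) were excluded from the study". Analgesic use is not among them, nor among the inclusion criteria (age, triage level 4 or 5, no disability or mental disorder, suitability for a 20 G antecubital cannula).

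Section 5 (Randomisation) stratifies by one factor: "The randomisation method was used by layering according to gender". Section 6 (Data Collection Tools) describes a form holding socio-demographic items and the VAS, and says that "VAS was used to evaluate pain caused by needle insertion". Section 9 (Data Analysis) names the t test and one-way ANOVA. Earlier analgesic use appears only in the one exclusion sentence.

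**The concern.** In a trial of needle pain one expects recent analgesic users to be kept out, because the drug could lower the rating whatever the arm. (That is an inference; the protocol does not say it.) Here the negation sits inside an exclusion rule, so *not* having taken an analgesic counts towards exclusion and having taken one can only help a patient qualify. The ungrouped *and ... or* adds a second doubt, since the eligible population changes with the grouping.

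If analgesic users entered in number, three things could be at stake: a noisier VAS, a smaller average contrast if distraction has less pain to relieve in users, and a sample that readers cannot describe. Analgesic use is neither a stratum nor among the data listed as collected, so the question might not be answerable afterwards.

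**Working it through.** **Step 1: what the sentence admits.** Let A = came for acute pain, B = analgesic within 24 hours, C = multiple earlier PIC procedures. All three come from the one sentence in section 3. The readings exclude a patient if:

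- Reading 1: (A and not B) or C, the ordinary grouping, in which *and* binds before *or*.
- Reading 2: A and (not B or C).
- Reading 3: A or not B or C, treating the sentence as a list of three separate exclusions.

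| A | B | C | Reading 1 | Reading 2 | Reading 3 |
|---|---|---|---|---|---|
| no | no | no | in | in | out |
| no | yes | no | in | in | in |
| yes | no | no | out | out | out |
| yes | yes | no | in | in | out |
| no | no | yes | out | in | out |
| no | yes | yes | out | in | out |
| yes | no | yes | out | out | out |
| yes | yes | yes | out | out | out |
| **Eligible of 8** | | | **3** | **5** | **1** |
| Users (B = yes), of 4 | | | 2 | 3 | 1 |
| Non-users (B = no), of 4 | | | 1 | 2 | 0 |

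With A and C held fixed, moving B from no to yes never turns *in* into *out*. It turns *out* into *in* once per reading. The observation about the wording is therefore correct. These are counts of profiles, not of patients: the protocol gives no frequency for A, B or C.

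**Step 2: would a misplaced *not* change much?** Delete it and keep the ordinary grouping: exclude if (A and B) or C. Eligible are (no, no, no), (no, yes, no) and (yes, no, no), again 3 of 8. Against Reading 1, one profile is swapped: acute pain with an analgesic leaves, and acute pain without one enters. An analgesic user without acute pain is eligible either way. So even this correction would not keep all users out.

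**Step 3: effect on the comparison between arms.** B is fixed before the patient reaches the emergency unit, hence before allocation. Whatever the screening rule was, the share of users is equal across the three arms of 40 in expectation. Chance imbalance is covered by the error rate of the test. Failing to stratify on B does not alter this.

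**Step 4: effect on precision.** The protocol gives no inputs, so all are assumed: user share p from 10% to 50%, rating lowered in users by δ = 0.5 to 1.5 cm, and VAS SD 2.0 to 2.5 cm within users and within non-users. The relative rise in SD is √(SD² + p(1 − p)δ²)/SD − 1.

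- p = 0.1, δ = 0.5, SD = 2.5: √(6.25 + 0.0225)/2.5 − 1 = 0.18%.
- p = 0.3, δ = 1.0, SD = 2.0: √(4 + 0.21)/2 − 1 = 2.6%.
- p = 0.5, δ = 1.5, SD = 2.0: √(4 + 0.5625)/2 − 1 = 6.8%.

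**Step 5: dilution.** If the distraction effect is smaller in users by a fraction r, the average effect shrinks by p × r: 0.10 × 0.25 = 2.5% up to 0.50 × 0.50 = 25%. The upper figure needs half the sample to be users and the effect halved in them. Nothing in the protocol supports such a difference.

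**The case for a change.** The best case for acting is that eligibility belongs in the protocol and cannot be left to an analysis plan. The protocol also takes care to hold other influences on needle pain constant: one cannula gauge, the left antecubital vein and one inserter. It thought analgesic use relevant enough to mention, yet wrote a clause that cannot exclude users and, read as a list, admits only them. Separating the three criteria and checking the screening records would cost little.

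Part of this stands. The sentence is poorly built, nothing else in the document settles it, and the protocol alone does not fully determine who was eligible.

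The rest is weaker. The users-only consequence depends on Reading 3, which needs *and* to mean *or* and describes an implausible target population. The claim that users ought to have been excluded is a preference: keeping out untreated acute pain is a sensible aim in itself, and the document does not establish a slip. The four reasons listed with n=98 prove little, because the text refers to Figure 1 for the participant flow and that figure is not shown here. Section 6 summarises the form and need not list every item. A sensitivity analysis by analgesic use could properly sit in a separate analysis plan, and may be impossible if the item was not recorded.

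**Conclusion.** The wording is ambiguous, and as written recent analgesic use never excludes a patient. The document does not show that the rule is wrong: its ordinary reading is coherent, and under any reading the randomised comparison between arms is unaffected in expectation. The likely cost is a small loss of precision, about 0.2% to 7% on the SD under wholly assumed inputs; the dilution figures depend on an effect difference for which there is no evidence. Recruitment is described as complete, so redrafting would not change who entered, how they were allocated or the planned tests.

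What remains is a matter of reporting. Whoever describes the enrolled population will have to state the rule applied at screening, and can do so without amending the plan and without presuming that users should have been kept out. This conclusion assumes that one rule was applied to all patients before allocation. The separate exclusion after a failed first insertion is a different question and is not judged here.

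### Assignment before insertion, exclusion of failed first insertions and a count of 120 throughout do not fit together; on the natural reading the groups are selected on an event after assignment

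*Protocol*

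**What the plan says.** - **Timing of assignment (Protocol section 2):** "Before the PIC insertion, the patients were assigned to three groups".
- **Start of the distraction (section 2):** the cards begin with the insertion procedure. For the virtual reality video: "This show, starting at the beginning of the procedure, lasted nearly 2-3 minutes".
- **Exclusions (section 3):** after refusal, unsuitability for a 20 G cannula and age, the list ends with patients "who could not be inserted PIC at the first time (n=98) were excluded from the study". The sentence refers to Figure 1, which is not available here.
- **Counts (sections 4 and 5):** "The study sample numbered 120 patients" and "Three groups of 40 patients each were generated, and 120 patients were randomised into the control or experimental groups". Section 3 also gives a sample of 120.
- **Operator and timing of ratings (section 7):** "All of the PIC insertion procedures were performed by the same researcher". A second researcher, unaware of the group, collected pain and satisfaction immediately after insertion.
- **Outcome (sections 1 and 6):** the first hypothesis is that the distractions "reduce pain associated with needle entry during the PIC procedure compared to the control group"; "VAS was used to evaluate pain caused by needle insertion". The second hypothesis concerns satisfaction with the procedure.

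**The concern.** Refusal, age and cannula suitability can be known at screening. Failure of the first insertion cannot: it is a result of the procedure. By section 2 the patient already has a group and the distraction is under way when it happens.

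Randomisation makes the groups comparable as assigned. If those whose first insertion failed are then removed, the comparison is among successes only. Success could differ by arm, because the patient is wearing goggles or answering questions about cards while the needle goes in. Patients who are hard to cannulate may also report different pain. Part of an observed difference in pain or satisfaction could then reflect who was left in each group rather than the distraction.

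**Working it through.** **1. The stated counts.** 3 × 40 = 120 randomised (section 5). The study sample is 120 (sections 3 and 4). 120 − 120 = 0, so the stated counts leave no room for any exclusion after randomisation.

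**2. The sequence.** Sections 2 and 7 give this order: assignment, start of procedure and distraction together, first attempt succeeds or fails, rating immediately afterwards. One researcher did every insertion and no earlier attempt is described, so the failed attempt is most naturally the study attempt.

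**3. Ways to make the statements agree.**
- *No assigned patient failed.* Possible, but it sits badly with failure being listed among exclusions that took place.
- *Failures were replaced or not counted.* Then 120 is not the number assigned, and section 5 is wrong as worded. This is the natural reading.
- *Failures came before assignment.* Section 2 does not support this, and it needs an attempt that the protocol never describes.

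**4. What a failure rate would imply (assumed; the protocol gives none).** With failure probability q, independent between patients, the chance of no failure among 120 is (1 − q)^120. The number to assign in order to retain 120 is 120/(1 − q), rounded up.

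| q (assumed) | Chance of no failure in 120 | Assigned to retain 120 |
|---|---|---|
| 2% | 0.089 | 123 |
| 5% | 0.002 | 127 |
| 10% | 0.000003 | 134 |
| 20% | below 0.000001 | 150 |

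**5. Possible size of the distortion (illustration only).** Assume no true effect, and let insertion difficulty and pain be standard normal with correlation ρ. The hardest fraction f fails and is removed. The mean pain of those retained is −ρφ(c)/(1 − f), where c is the upper-f normal quantile. Example with ρ = 0.5:
- f = 10%: φ(c)/(1 − f) = 0.1755/0.9 = 0.19500
- f = 20%: φ(c)/(1 − f) = 0.27996/0.8 = 0.34995
- Difference 0.15495; times 0.5 = 0.077 SD

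False-positive rates are from the noncentral t, 40 against 40, two-sided 0.05.

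| Failure in the two arms (assumed) | Shift, ρ = 0.3 | Shift, ρ = 0.5 | False positives |
|---|---|---|---|
| 5% and 10% | 0.026 SD | 0.043 SD | 5.2% to 5.4% |
| 10% and 20% | 0.046 SD | 0.077 SD | 5.5% to 6.5% |
| 10% and 30% | 0.091 SD | 0.151 SD | 6.9% to 10.8% |
| 10% in both, ρ = 0 in one arm | 0.058 SD | 0.097 SD | 5.8% to 7.2% |
| 20% in both, ρ = 0 in one arm | not run | 0.175 SD | 12.1% to 12.5% |

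Most of these shifts are small. A negative ρ, or exchanging the arms, reverses the sign. Equal failure rates do not guarantee no shift if different kinds of patients fail in each arm.

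**The case against.** The strongest reply is that section 3 describes screening. Failed insertion stands in one list with three reasons known before assignment, the list points to the flow diagram, and the CONSORT checklist was followed. Ninety-eight excluded first and 120 randomised afterwards would make the counts consistent. This cannot be ruled out, and Figure 1 may settle the counts. But it goes against the timing in section 2, and the text would still need to be brought into line.

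A second reply is that a single successful stick keeps the stimulus uniform. That is a reasonable aim, and it has weight for satisfaction, and for pain rated over the whole procedure, which after a failure may reflect more than one stick. It has less weight for pain on needle entry, which also occurs in a failed attempt. It does not undo the selection in either case.

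A third reply is that the bias may be negligible. That stands as far as it goes: several rows of the illustration are close to 5%, and all its inputs are assumed.

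Three stronger inferences are tempting and are not supported:
- *That 98 first attempts failed*, so that 120 + 98 = 218 were assigned and 98/218 = 45% were dropped. The figure follows the last item of a four-item list and probably totals all four reasons, but its scope is ambiguous. Neither the number of failures nor the number assigned, nor a range for them, can be derived from it.
- *That the result favours the distraction.* The direction depends on which arm had more failures and on how those patients would have rated pain; the text gives neither.
- *That neither outcome needs the exclusion.* This can be argued for needle-entry pain only.

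**Conclusion.** The point holds as a conflict in the protocol's own statements, with a likely consequence for the comparison. Assignment before insertion, exclusion for a failed first insertion, and 120 both randomised and in the sample cannot all stand without a rule that the text does not state. On the natural reading, the analysed groups are conditioned on first-attempt success and are not the groups as randomised.

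This reading rests on the failed attempt being the study attempt, which sections 2 and 7 support but do not state outright. That a bias exists is not shown. Its size and direction cannot be determined from the text, and it may be small. The passages should be corrected, with medium confidence that the exclusion came after assignment.

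**What to change.** Reconcile sections 2, 3 and 5. Unless Figure 1 already does so, state:
- when failed first insertions occurred relative to assignment;
- the number assigned and the number of failures in each arm;
- whether failures were replaced or left out of the randomised count;
- which reasons the 98 covers.

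Then, according to what was recorded:
- **Needle-entry pain ratings exist for failed first attempts:** make the primary pain comparison on all assigned patients in their assigned group, with first-attempt successes as a sensitivity analysis. Treat satisfaction likewise where it was rated, noting that it may reflect more than one stick.
- **No such ratings exist:** limit the conclusion to patients with a successful first attempt and, using the failures by arm, add a sensitivity analysis for the missing ratings. Extreme-value bounds alone would be wide: with an assumed 10% missing in each of two arms, their width on the 0 to 10 scale is 0.1 × 10 + 0.1 × 10 = 2 points. Milder assumptions should be shown beside them.
- **Failures preceded assignment:** say so, correct section 2, and the concern falls away.

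The study period ended on April 30, 2018, so ratings cannot be added. The cost is wording, counts from existing records and a reanalysis. The downside is a somewhat larger variance, or a narrower conclusion and a less favourable participant flow.

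### The sample size line gives β=0.10 and power 0.95 for one calculation, and 117 patients cannot be reproduced from d=1.60 if that is a standardised effect size

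*Protocol*

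**What the plan says.** Section 4 (Sample Size Calculation) names an online calculator and reports that "it was determined that a minimum of 117 patients were" "needed [d (effect size/ effect width) =1.60, α =0.05, β =0.10, and power=0.95". It then adds: "The study sample numbered 120 patients". The line gives no SD, unit, endpoint, sidedness, test or number of comparisons.

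Section 5 (Randomisation) gives the allocation: "Three groups of 40 patients each were generated". The planned minimum therefore corresponds to 117/3 = 39 per group.

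Two other places bear on the reading. Section 6 (Data Collection Tools) sets the pain scale ("In the VAS of 10 cm length"), so 1.60 could be a difference in cm. Section 9 (Data Analysis) names both a t test and one-way ANOVA, so the test behind 117 cannot be identified from there.

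**The concern.** There are two separate problems in one line.

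- **β and power contradict each other.** They are complements, so "β =0.10, and power=0.95" describes two different calculations. The type II error is either 10% or 5%, a factor of two, and the reader is not told which one the 117 patients were meant to secure.
- **The effect size does not lead to 117 if it is standardised.** The label is "d (effect size/ effect width) =1.60". Its first term points to a standardised difference, and 1.60 SD is so large that a few dozen patients would be enough. Its second term leaves room for a raw difference, but that reading needs an SD, which is not printed.

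This is the protocol's only justification of its size. A reader faced with a non-significant comparison needs to know which difference the trial could detect, and with what probability. The line does not say whether that difference is 1.60 SD or 1.60 cm, or whether the probability is 90% or 95%.

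**Working it through.** **Inputs from the protocol.** d=1.60, α=0.05, β=0.10, power=0.95, minimum 117 (all section 4); three groups of 40 (section 5). **Assumed here:** two-sided α and equal group sizes. Unless noted, comparisons are unadjusted.

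**Step 1: β against power.** 1 − 0.10 = 0.90, not 0.95; 1 − 0.95 = 0.05, not 0.10. No assumption is needed.

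**Step 2: try to reproduce 117 with d=1.60 standardised.** The normal approximation is n per group = 2(z₀.₉₇₅ + z_power)²/d².

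- 90%: 2(1.960 + 1.282)²/1.60² = 8.2, so 9 per group and 27 in total.
- 95%: 2(1.960 + 1.645)²/1.60² = 10.2, so 11 per group and 33 in total.

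The exact calculation (noncentral t) gives 9.28 and 11.21 per group, rounded up to 10 and 12.

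| Method, d=1.60 standardised | Total at 90% | Total at 95% |
|---|---|---|
| t test, exact | 30 | 36 |
| ANOVA, means equally spaced (f = 1.60/√6 = 0.653) | 33 | 42 |
| ANOVA, one group differs (f = 1.60·√2/3 = 0.754) | 27 | 33 |
| t test, α = 0.05/3 | 39 | 45 |

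One-sided tests and taking f itself as 1.60 give smaller totals still, down to 9. Nothing approaches 117. With 39 per group and d=1.60, power exceeds 0.9999, which matches neither stated value.

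**Step 3: solve backwards from 39 per group.** This gives the standardised difference that 39 per group detects, and the SD that would make a raw 1.60 cm equal to it (SD = 1.60/d). All these SDs are assumptions.

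| Method | d at 90% | SD, cm | d at 95% | SD, cm |
|---|---|---|---|---|
| t test, α=0.05 | 0.744 | 2.15 | 0.827 | 1.94 |
| t test, α=0.05/3 | 0.848 | 1.89 | 0.932 | 1.72 |
| ANOVA, equally spaced | 0.816 | 1.96 | 0.902 | 1.77 |
| ANOVA, one group differs | 0.707 | 2.26 | 0.781 | 2.05 |

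So 117 could follow from a raw difference of 1.60 cm with an SD somewhere between about 1.7 and 2.3 cm.

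**Step 4: what the contradiction is worth.** Hold the planned difference at the value that 39 per group detects, then change the power.

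| If 117 was sized for | Power with 40 per group | Total needed for the other stated power |
|---|---|---|
| 90% (d=0.744) | 90.7% | 95%: 47.99 per group, so 144 (ANOVA also 144) |
| 95% (d=0.827) | 95.5% | 90%: 31.7 per group, so 96 (ANOVA 99) |

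**Step 5: what 40 per group delivers.** By unadjusted two-sided t test against control, the detectable standardised difference is 0.734 at 90% power and 0.816 at 95%. If 1.60 is in cm, these correspond to SDs of up to 1.60/0.734 = 2.18 cm and 1.60/0.816 = 1.96 cm.

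**The case against.** The β and power contradiction has no defence in the text. The case on the other side concerns the rest.

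- **The label carries two terms.** On a 10 cm scale, reading 1.60 as centimetres is natural, and the SD it then needs is not implausible. This stands: the comparison of 27 to 42 patients with 117 holds only if d is standardised, and must not be read as proof that 117 is wrong.
- **The missing SD may be in an analysis plan that is not at hand, or in the calculator's output.** This is possible. But the protocol chose to print the inputs, and as printed they contradict each other and leave 1.60 undefined. That is a fault in the line itself.
- **Nothing in the conduct of the trial changes.** The protocol reports 120 patients randomised, above the stated minimum. Both 90% and 95% are conventional targets, and on the standardised reading there are more patients than needed. All true, and it is why the remedy is textual. Exceeding 117 still does not tell the reader which power 117 was meant to give.
- **The SD range depends on a two-sided test.** The hypotheses in section 1 are directional. A one-sided unadjusted t test with 39 per group at 90% power gives an SD of 2.39 cm, slightly outside the range above. This is fair, but it does not rescue 117 under a standardised 1.60, where one-sided tests need even fewer patients.

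**Conclusion.** The concern holds. The stated β and power are incompatible, whatever is assumed about the effect. Depending on which value drove the calculation, the 120 patients give about 91% or about 95% power for the planned difference. In the first case, the stated 95% is overstated and would need about 144 patients.

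The second part is conditional. If 1.60 is standardised, 117 is roughly three to four times what the inputs require (117/42 = 2.8 to 117/27 = 4.3). If 1.60 is in cm, 117 is attainable, but only with an SD that the line does not give. The document does not allow a choice between these readings, so the figure is unverified, not refuted. On neither reading does this point alone call for more patients; the exception would be if 117 was sized for 90% and the sponsor wished to claim 95%.

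**What to change.** Keep the 120 patients and rewrite the sentence in section 4, using the calculator's actual inputs:

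1. State one consistent pair: β=0.10 with power 0.90, or β=0.05 with power 0.95.
2. State whether 1.60 is a standardised difference or a difference in cm on the pain scale. If it is in cm, give the SD used. Name the endpoint, the test and the sidedness behind 117.
3. Restate what 40 per group delivers. For example, per unadjusted two-sided comparison with control: 90% power for a standardised difference of 0.73, or 95% for 0.82. If 1.60 is in cm, this means SDs of up to 2.18 cm or 1.96 cm respectively.

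The cost is one rewritten sentence, with no extra patients and no change to the analysis. The stated power or effect size may turn out less favourable than the one now printed.

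### Randomisation is stratified by gender, but the named tests have no gender term; if gender predicts the outcome they are mildly conservative and forgo a small gain in precision

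*Protocol*

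**What the plan says.** Section 5 (Randomisation) fixes the design: "The randomisation method was used by layering according to gender" and "Three groups of 40 patients each were generated, and 120 patients were randomised into the control or experimental groups". It does not describe blocking within the gender strata.

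Section 9 (Data Analysis) fixes the comparison: "T test and One way ANOVA were used in comparative statistics", with p < 0.05 as the level that "level was accepted as an indication of significant difference in statistical decisions". It names no covariate, two-way ANOVA, ANCOVA or stratified test, and neither does any other section. It does not say which groups the t test compares.

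The outcomes are a 0 to 10 pain VAS and a 1 to 10 satisfaction score (section 6), both summarised by means and standard deviations. The protocol gives no gender mix and no figure for how strongly gender relates to either outcome.

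**The concern.** Stratifying treats gender as worth balancing, and the analysis then ignores it. With gender balanced across arms, gender differences cannot contribute to the difference between arm means. The unadjusted t test and ANOVA still count those differences in the within-arm variance, so they overstate the uncertainty of the comparison.

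The error is on the safe side. What is at stake is a true significance level below the stated 5%, confidence intervals that are somewhat too wide, and a small amount of power that the design has made available and the analysis does not use.

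**Working it through.** **Inputs from the protocol.** 40 patients per arm, stratification by gender (section 5); decisions at 0.05 (section 9), taken as two-sided for the t test. The t test is read as one method against control.

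**Assumed, because the protocol does not state it.** Normal outcome; exactly 20 men and 20 women per arm; a gender difference of δ within-gender SDs, with δ = 0.3, 0.5, 0.8 or 1.0.

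**The protocol's own figure and the scale of effect.** Section 4 gives "effect size/ effect width) =1.60" with "α =0.05, β =0.10, and power=0.95" and a minimum of 117. Read as a standardised difference, 1.60 needs only 7 to 13 per arm (21 to 39 in total) over one- and two-sided tests, 90% or 95% power and alpha from 0.0167 to 0.05, so 117 is not reproduced. At 39 per arm and two-sided 0.05 it is reached if 1.60 is a raw difference with an SD of about 2.18 (90% power) or 1.96 (95% power):

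- 1.60 / 2.18 = 0.73 SD
- 1.60 / 1.96 = 0.82 SD

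These two effects are used below, in units of the overall SD. The clash between β and power is a separate matter, and nothing here depends on resolving it.

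**Mechanism.** Let σ be the within-gender SD. With a 20/20 split, gender adds δ²/4 to the within-arm variance.

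- Share of variance due to gender: (δ²/4) / (1 + δ²/4). For δ = 0.5: 0.0625 / 1.0625 = 5.9%.
- True standard error of a two-arm difference: σ√(2/40) = 0.224σ.
- Standard error the t test uses, approximately: 0.224σ × √(1 + δ²/4). For δ = 0.5: 0.224σ × 1.031, which is 3.1% too large.
- Large-sample true level: 2[1 − Φ(1.96 × √(1 + δ²/4))]. For δ = 0.5: 2[1 − Φ(2.020)] = 4.3%.

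The t-test figures in the table are exact. The unadjusted residual sum of squares is noncentral chi-square with 78 df and noncentrality 80 × 0.25 × δ²; the adjusted test is a noncentral t with 77 df. The ANOVA figures come from 60,000 simulated three-arm trials per setting.

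| Gender difference δ (SD) | 0.3 | 0.5 | 0.8 | 1.0 |
|---|---|---|---|---|
| Share of variance | 2% | 6% | 14% | 20% |
| Standard error too large by | 1.1% | 3.1% | 7.7% | 11.8% |
| True level, t test without gender | 4.75% | 4.33% | 3.48% | 2.84% |
| True level, ANOVA without gender | 4.6% | 4.2% | 3.0% | 2.4% |
| t-test power at 0.73 SD, without gender | 89.9% | 90.3% | 91.2% | 92.0% |
| t-test power at 0.73 SD, with gender | 90.3% | 91.4% | 93.5% | 95.0% |
| ANOVA power, both methods shifted 0.73 SD, without gender | 92.7% | 93.2% | 93.5% | 94.1% |
| ANOVA power, both methods shifted 0.73 SD, with gender | 93.1% | 94.2% | 95.8% | 96.9% |

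With gender in the model the true level is about 5.0% in every column.

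**Other settings.**

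- At 0.82 SD the gain in t-test power is 0.2 to 1.4 points.
- At 1.60 SD both analyses exceed 99.9% power and there is nothing to gain.
- At an assumed smaller effect of 0.5 SD, t-test power is 60.0% against 62.4% for δ = 0.5, and 60.7% against 69.5% for δ = 1.0.
- With a 70/30 gender mix, the t test's true level runs from 4.8% (δ = 0.3) to about 3.1% (δ = 1.0).
- With gender balance left to chance (40,000 simulated two-arm trials per setting), the unadjusted t test holds 4.9% to 5.2%. Adjustment still raises power at 0.73 SD, from 89.7% to 89.9% at δ = 0.3 and from 89.6% to 94.8% at δ = 1.0.
- With no gender effect, power at 0.73 SD is 89.7% either way.

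**The case against.** The unadjusted tests are valid. They are unbiased, do not inflate false positives and do not fall below their planned power, so it can be argued that nothing is fixed badly. That argument limits the severity. It does not remove the point, because the analysis omits the factor the design was stratified on.

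Covariates are often left to an SAP, and one may exist. Here, however, the document's subtitle covers the data analysis as well as the protocol, and section 9 names the tests and the decision rule. Adding gender changes a stated method rather than supplying a missing detail.

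The loss of level needs a second condition besides a gender effect: gender must be balanced in the patients analysed. Section 5 describes no blocking within strata, and section 3 excludes patients whose first insertion attempt failed, which may act after allocation. This stands. Without balance the level returns to about 5%, although adjustment still adds power.

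The upper end of the range is demanding. If 1.60 is a raw difference with an overall SD of 1.96 to 2.18, a gender gap of 1.0 within-gender SD is 1.96/1.118 = 1.75 to 2.18/1.118 = 1.95 points, more than the effect the trial was sized for. This also stands, and 0.3 to 0.5 SD is the better range to lead with.

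Finally, section 9 is written in the past tense. If the outcomes have already been analysed, making the adjusted model primary is a change after the fact. The choice of covariate is nevertheless set by the randomisation and not by the results.

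**Conclusion.** The concern holds as a small, conditional point about efficiency. If gender predicts pain or satisfaction and is balanced across the analysed arms, the tests in section 9 are conservative. At a gender difference of 0.3 to 0.5 SD the effect is slight: a true level of 4.2% to 4.8% across the two tests, and a gain of about 1 power point or less at 0.73 SD. At 0.8 to 1.0 SD it is moderate: a level of 2.4% to 3.5%, and a gain of 2 to 3 points.

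The power gain is zero if gender has no effect, and also if 1.60 is a standardised difference. All sizes rest on an assumed gender effect, normal outcomes and, for the t test, a two-sided comparison of one method with control. The trial's validity is not in question.

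**What to change.** State in section 9 that pain and satisfaction are each compared with a linear model containing group (three levels) and gender as fixed factors, without interaction, and that each method-versus-control contrast is taken from that model. Keep the unadjusted one-way ANOVA and t tests as a sensitivity analysis. Date the change and say whether outcome data had been seen; if they had, show both analyses side by side.

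The cost is one added factor in the SPSS general linear model and one degree of freedom. Gender is already recorded for every patient through the stratified randomisation, so no further data or patients are needed.
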